2.2. Overview of MTR-601

MTR-601 is a small-molecule inhibitor of myosin-2 “fast” isoforms being developed by Motric Bio, Inc. (Motric) for the treatment of muscle spasticity associated with neurological injury or disease. MTR-601 selectively stabilizes the actin unbound conformation of myosin-2 isoforms that have a leucine at position 476 instead of a phenylalanine. Selective targeting is essential as myosin isoforms in skeletal muscle and heart muscle are structurally similar. The selectivity of MTR-601 spares “slow” isoforms found in cardiac and smooth muscle [4].

The proposed MTR-601 development program relies on prior nonclinical data acquired from Motor Pharma who began development of the investigational compound (known to Motor Pharma as MPH-220) as well as nonclinical studies sponsored by Motric. Nonclinical studies

have indicated that MTR-601 selectively inhibits fast skeletal myosin-2. As such, it can reduce skeletal muscle force in healthy rats and improve spasticity and gait in rat models of brain injury. Further, it reduces generalized muscle contractions and the consequent muscle damage in epilepsy models at doses shown to be safe and tolerable in preliminary non-GLP dose-range-finding (DRF) toxicology studies. A full package of nonclinical safety pharmacology and toxicology studies is ongoing for MTR-601 via the oral gavage route and in compliance with International Council for Harmonisation (ICH) M3(R2) guidelines. Additional supporting in vitro pharmacology and drug metabolism and pharmacokinetic (PK) studies will also be included in the initial IND submission. Proposed study MTR601-NHV-101 will be the first-in-human (FIH) study for MTR-601 to be conducted in normal, healthy volunteers. Later development will focus on conditions characterized by hypertonia and/or spasticity such as, but not exclusively, cerebral palsy, in multiple age ranges.

2.3. Nonclinical Studies and Interim Safety Analysis

Refer to the Investigator's Brochure (IB) or MTR-601 regarding nonclinical study data.

An unblinded interim safety analysis of SAD cohorts 1-4 and MAD cohorts 1-3 was performed to support further dose escalation above the 1/10th rat 28-day NOAEL level (where MAD dosing had been capped by the FDA). The key conclusions from that interim analysis were:

- In either single doses (10, 20, 40 and 80 mg) or repeat daily doses (10 and 20 mg for 14 days) MTR-601 did not demonstrate pharmacodynamic evidence of decreased muscle strength. This is likely because the achieved muscle concentrations (≤ 937 ng/mL) were below the estimated target for efficacy ($\geq 3,000$ ng/dL). Further dose escalation is required to adequately characterize MTR-601's pharmacodynamic effect.
- In both single and multiple doses, MTR-601 plasma pharmacokinetics were consistent and predictable, with linear dose-exposure proportionality, and modest (<2 -fold) accumulation at steady state. At the 20 mg level, steady state exposure (C_{max} and AUC_{0-24}) was approximately 1/15th of the NOAEL. MTR-601's well-behaved pharmacokinetics allows for reliable prediction of exposure for careful, continued dose escalation.
- In both single and multiple doses, MTR-601 was safe and very well tolerated, with no treatment-related AEs, and no clinically significant laboratory, ECG, or vital sign abnormalities. There were no MTR-601 associated abnormalities in plasma or urine markers of kidney function, and no objective or subjective evidence of urinary obstruction. This very good safety profile justifies continued dose escalation to more fully characterize MTR-601's clinical profile.

The findings of the interim safety evaluation support continued dose escalation to more fully characterize the PK, PD and safety of MTR-601.

2.4. Study Rationale

MTR-601 is an oral, small-molecule drug intended to selectively inhibit the isoform of myosin-2 found in fast-twitch skeletal muscle but not the myosin isoforms found in smooth or cardiac

muscle. The clinical objective is to reduce hypertonicity and spasticity in skeletal muscle from primary muscular disease and/or secondary to neurologic injury.

The current study is a FIH evaluation of MTR-601 and focuses on the safety, tolerability, and pharmacokinetics (including uptake into skeletal muscle) of the drug in normal healthy volunteers. Exploratory assessments of effects on the force of muscular contraction will also be performed and evaluated as it relates to dose, exposure, and/or muscle accumulation with potential adjustments for total body muscle mass.

As a FIH study, this will be conducted in normal healthy volunteers in the fed state, with further evaluation of food effect in SAD dose level 2, as nonclinical studies have indicated that food increases drug exposure.

The evaluations of effects on muscular contraction with potential adjustments for total body muscle mass will help guide dosing selection in adult and potential pediatric patient populations in subsequent clinical studies.

2.5. Benefit/Risk Assessment

There will be no direct benefits to normal healthy volunteers being enrolled in this FIH study.

Safety is predicated on the enabling, nonclinical Good Laboratory Practice (GLP) safety and toxicology studies. In addition, during the clinical study, extensive safety evaluations of biochemical, hematologic, renal and urinary systems, cardio-respiratory parameters, as well as clinical evaluations, will be performed. A two-stage dosing strategy with sentinel participants will limit exposure to the investigational agent as dosing is advanced.

To fully evaluate the PK and pharmacodynamic (PD) aspects of MTR-601, subject's will be asked to undergo a single needle biopsy of skeletal muscle (vastus lateralis) using a Bard Magnum 12 gauge or functionally similar hand-held, spring-loaded device (in conjunction with local anesthesia and skin disinfection), potentially requiring 2 collections, which is minimally invasive and commonly used in clinical trials. The risks of such a procedure are discomfort/pain and possibly some small post-procedure bleeding. Any adverse reactions will be appropriately attended to by the unit medical staff.

The myosin-2 isoform is present in fast-twitch skeletal muscles and the extra-ocular muscles could be affected by MTR-601. Oculofacial AEs or any reduction in movement of the eyes, with potential for disconjugate gaze and/or possible "dizziness" or "imbalance" will be noted as an AESI. Additionally, AEs relating to swallowing or proximal muscle weakness (evaluated as part of the routine neurological examination) will be noted as an AESI. Nonclinical studies in the rat but not the dog showed urinary symptomatology not expected in humans, but out of an abundance of caution, any AE relating to difficulties in urination (evaluated with the IPSS questionnaire and urinary system ultrasound) will be noted as an AESI.

3. OBJECTIVES AND ENDPOINTS

Objectives	Endpoints
Primary	
To assess the safety and tolerability of single and multiple doses of MTR-601 in normal healthy volunteers under fed and fasted conditions.	
The primary endpoint is safety assessed after single and multiple dose administration by:
 
 • Incidence, severity, and relatedness of adverse events (AEs; number and incidence of treatment-emergent adverse events [TEAEs]) • Incidence of laboratory abnormalities, based on hematology, clinical chemistry, coagulation, urinalysis test results • Vital sign measurements • 12-lead electrocardiograms (ECGs) • Echocardiography • Physical and neurological examinations • Telemetry and oximetry • Spirometry • Urinary system Ultrasound
Secondary	
To evaluate the plasma and urine pharmacokinetics (PK) of MTR-601	
Pharmacokinetic evaluations may include:
 
 • Concentration-time relationships • Estimations of dose proportionality at steady state • Estimation of time to achieve steady state • Potential MTR-601 metabolites
	
Exploratory	

Muscle accumulation of MTR-601 by muscle biopsy and other potential mechanistic, predictive and PD markers of MTR-601	
• An evaluation of concentration-effect relationships with other parameters (e.g., cytochrome P450 isoenzymes that affect absorption, distribution, metabolism, and excretion [ADME], other muscle parameters, gender, etc.) that may be performed at a later date and described in a stand-alone analysis plan and report• Muscle accumulation assessed by muscle biopsy and estimates of body muscle mass• An evaluation of potential MTR-601 PD and/or predictive biomarkers may be conducted (genetic and/or protein endpoints)
---	---

4. STUDY DESIGN

4.1. Overall Design

This randomized, placebo-controlled, FIH study of MTR-601 in normal healthy volunteers will consist of 5 single ascending dose (SAD) level cohorts (including 1 SAD Level 2 Two-Dose cohort), and up to 6 multiple ascending dose (MAD) level cohorts, each comprised of 8 subjects (6 MTR-601; 2 placebo). The total sample size will be up to 88 subjects to accommodate withdrawal of consent or replacement for other non-TEAE reasons.

Table 4: SAD/MAD Dose Level Cohorts

SAD/MAD Cohort ^{a & b}	Dose ^g	Fasted	Fed Standard ^c	N ^e
SAD Level 1	10 mg		✓	8 ^f
SAD Level 2, Two-Dose ^d	20 mg	✓	✓	8 ^f
SAD Level 3	40 mg		✓	8 ^f
SAD Level 4 (Optional)	80 mg		✓	8 ^f
SAD Level 5	160 mg		✓	8
MAD Level 1	10 mg		✓	8
MAD Level 2	20 mg		✓	8
MAD Level 3	20 mg		✓	8
MAD Level 4	40 mg		✓	8
MAD Level 5	80 mg		✓	8
MAD Level 6	≤160 mg		✓	8

Abbreviations: MAD = multiple ascending dose; N = number of subjects; SAD = single ascending dose. Fasted: Subjects will remain NPO (clear liquids allowed) for at least 8 hours prior to dosing.

- Subjects will participate in only 1 dose level cohort in either the SAD, Two-Dose, or MAD portions of the study.
- All subjects, regardless of cohort, will have doses administered with staggered timing such that no subjects shall be dosed simultaneously.
- Subjects will be fed a standard (not high-fat) breakfast 30 minutes before dosing.
- Subjects in the SAD Level 2, Two-Dose cohort: For the first dose, subjects will be fasting; for the second dose, subjects will be fed a standard not-high fat breakfast 30 minutes before dosing.
- 6 MTR-601 and 2 placebo per cohort.
- All SAD dose cohorts (including Level 2, Two-Dose) will have 2 sentinel subjects followed at least 72 hours later by the remaining 6 subjects.
- Cohort dose may be modified by the Sponsor based upon pharmacokinetic and safety results from earlier cohorts.

SAD Levels 1–5 dosing:

- Each of the SAD dose level cohorts will have 2 sentinel subjects followed at least 72 hours later by the remaining 6 subjects in 1 or more groups, in a staggered fashion. Both sentinel subjects will be evaluated for 72 hours by the Investigator for safety prior to dosing the cohort's remaining 6 subjects.
- Dosing will begin at dose Level 1 (10 mg).

- Subjects in SAD Levels 1, 3, 4 and 5 will be dosed in a fed state (standard non-high-fat breakfast).
- Subjects in the SAD Level 2 Two-Dose (20mg) will be dosed in a fasting state on Day 1 with a subsequent 4-day washout period, followed by dosing in a fed state (standard not-high fat breakfast) on Day 6.
- SAD Level 4 (80 mg) dosing is optional and may be adjusted based upon PK and safety results from earlier cohorts.
- Subjects may be enrolled in small groups to accommodate clinic scheduling.

MAD Levels 1–6 dosing:

- The MAD portion of the study will commence at MAD Level 1 (10 mg) after the safe completion of the subjects in at least the 2 SAD Level 2 Two-Dose cohort.
- Subjects in MAD Levels 1–6 will be dosed in a fed state (standard non-high-fat breakfast) over 14 continuous days of dosing.
- MAD cohorts may be enrolled in small groups to accommodate clinic scheduling with subjects dosed in a staggered fashion.

Dose Escalation:

The study will be monitored by a Safety Review Committee (SRC) comprised of the Principal Investigator (PI), the Medical Monitor, and the Sponsor. The SRC is intended to ensure treatment does not pose undue risk to subjects. Dose escalation to the next higher dose level cohort will not take place until the SRC has assessed the data from at least 7 out of 8 subjects/cohort through discharge (supplemental plasma PK information on a previously treated cohort may be requested as a part of the review) and determined that adequate safety and tolerability has been demonstrated to permit proceeding.

The planned dose levels for MAD Cohort 5 (80 mg) and Cohort 6 (160 mg) may be decreased based on the plasma PK from the preceding MAD cohort. Escalation will proceed no higher than a dose that is estimated to yield $\leq \frac{1}{2}$ of the rate 28-day NOAEL exposure ($C_{\max} \leq 421$ ng/mL, $AUC_{0-24} \leq 6,600$ ng*hr/mL).

The SRC may recommend:

- Ascending to the planned next higher dose level
- Ascending to a dose level lower than the planned next higher dosage level cohort
- Repeat dosing at the current dose level
- Descending to an intermediate dose above a previously tolerated dose level
- Pausing dose escalation
- Stopping the study

Participation in the clinical study may be discontinued by an Investigator (or delegate) in charge of the study or by the Sponsor for any of the following reasons in [Table 5](#).

Table 5: Stopping Rules

Stopping Rules ^d	Individual Subject Stopping Rules ^a	Cohort and/or Dose Escalation Stopping Rules
ALT or AST $\geq 3 \times$ ULN	≥ 1 subject	N/A
ALT or AST $> 5 \times$ ULN	N/A	≥ 2 subjects
Creatinine $> 1.2 \times$ ULN or an increase in serum creatinine by $\geq 30 \mu\text{mol/L}$ within 24 hours or an increase in serum creatinine to $\geq 1.5 \times$ baseline within 7 days	≥ 1 subject	≥ 2 subjects
QTcB and QTcF > 500 msec or change from baseline: QTc > 60 msec	≥ 1 subject	≥ 2 subjects
Sustained heart rate < 45 bpm or heart rate > 130 bpm ^b confirmed by repeat after 30 minutes	≥ 1 subject	≥ 2 subjects
Sustained systolic blood pressure < 80 or systolic blood pressure > 155 mmHg confirmed by repeat after 30 minutes	≥ 1 subject	≥ 2 subjects
Sustained diastolic blood pressure > 100 mmHg confirmed by repeat after 30 minutes	≥ 1 subject	≥ 2 subjects
Occurrence of a serious adverse event (SAE) in a participant not receiving placebo	≥ 1 subject	≥ 1 subject
Severe AEs in the same cohort	N/A	≥ 1 subject
Clinically significant laboratory abnormalities of the same character	N/A	≥ 2 subjects
Confirmed lower urinary tract obstruction ^c (Two successive post-void residual volume determinations within 24 hours exceeding 100 mL) or evidence of hydronephrosis upon Ultrasound evaluation.	≥ 1 subject	≥ 1 subjects
A drop in the eGFR below 70 mL/min/1.73 m ² (CKD-EPI) or a reduction of 25% from baseline.	≥ 1 subject	≥ 2 subjects
A confirmed ^e reduction in the FVC (forced vital capacity done in triplicate) to less than 80% of the predicted vital capacity based on gender, height and age with good expiratory effort as assessed by the Investigator	≥ 1 subject	≥ 2 subjects
Any subject who develops gross or microscopic (> 5 RBC/HPF) hematuria (unless clearly caused by menses)	≥ 1 subject	≥ 2 subjects
Any subject who has signs, symptoms, and urinalysis/dipstick evidence of a clinically significant urinary tract infection	≥ 1 subject	≥ 2 subjects

Abbreviations: AE = adverse event; ALT = alanine aminotransferase; AST = aspartate aminotransferase; bpm = beats per minute; mmHg= millimeters of mercury; msec = millisecond; IP = investigational product; N/A = not applicable; QTcB= QT correct with Bazett formula; QTcF = QT interval corrected for heart rate using Fridericia's formula ;ULN = upper limit of normal.

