1.5. Schedule of Assessments (MAD)

Table 3: Schedule of Assessments Multiple Ascending Dose Level Cohorts 1 – 6 (MAD) – Screening/Check-in/Day 1

	Screening	CI	CRU Inpatient										
Day	(-30 to -2)	D (-1)	D1 – Initial Dosing Day										
Hour			0	0.25	0.50	1	1.5	2	3	4	6	8	12
Informed consent	X												
Confirm eligibility	X	X ^o											
Demographics	X												
Medical history	X	X											
Full physical examination	X	X											
Neurological examination	X	X											
Height/weight ^a	X	X											
HIV/Hep B/Hep C	X												
CRU Check-in		X											
SARS-CoV-2 PCR ^b		X											
Drug screen ^c	X	X											
Laboratory assessments ^d	X	X								X			X
Urinalysis ^e	X	X								X			
FSH testing ^f	X												
Pregnancy test ^g	X	X											
12-lead electrocardiogram	X	X											
Body composition ^h		X											
C-SSRS	X	X											
LVEF/Echocardiogram	X ⁱ												
Randomization			X										
Cardiac telemetry ^j			←										
Oximetry ^j			←										

	Screening	CI	CRU Inpatient										
Day	(-30 to -2)	D (-1)	D1 – Initial Dosing Day										
Hour			0	0.25	0.50	1	1.5	2	3	4	6	8	12
Vital signs	X	X	X			X	X			X	X	X	X
Plasma PK ^k													
Urine PK ^l			X							X		X	X
Genetic biomarker (buccal swab)		X											
Plasma Biomarker			X			X							
Spirometry		X								X			X
Magnetic stimulated contraction ^p		X								X			
Dynamometry ^p		X								X		X	X
IPSS ^m		X											
Urinary system Ultrasound ⁿ		X											
MTR-601 administration			X										
Adverse events													
Concomitant medications	X	X											

Abbreviations: AE = adverse event; CI = Check-in; CK-MB = creatinine kinase heart; CK-MM = creatinine kinase skeletal muscle; C-SSRS = Columbia Suicide Severity Rating Scale; D = Day; LVEF = left ventricular ejection fraction; PK = pharmacokinetics.

Note: When several assessments overlap, the suggested sequence of events will be as follows: ECG, vital sign collection, PK sample collection, laboratory blood sample collections, spirometry, dynamometry, urinalysis sample collection, and biopsy, such that PK sample collection will be drawn as close to the nominal collection time point as possible.

- Height measured only at screening.
- To be performed as part of check-in procedures, prior to other Day -1 activities.
- Urine drug screen for cotinine, alcohol, and drugs of abuse.

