Table 3 continued... Schedule of Assessments Multiple Ascending Dose Level Cohorts 1–6 (MAD) – Days 2-18 and Follow-up

	CRU Inpatient																FU
Day	Non-PK Days 2–6, 8–13	PK Days 7 and 14											D15	D16	D17	D18	D20
Hour		0	0.25	0.50	1	1.5	2	3	4	6	8	12	0	0	0	0	4
Full physical examination		X														X	
Neurological exam		X														X	
Height/weight ^a		X														X	
Laboratory assessments ^b	X ^k	X											X	X	X	X	
Urinalysis		X											X	X	X	X	
12-lead ECG		X														X	
C-SSRS									X							X	
LVEF/Echocardiogram	X ^c																
Cardiac telemetry ^d																	
Oximetry ^d																	
Vital signs		X			X	X			X	X	X	X	X	X	X	X	
Plasma PK ^e													X	X	X	X	
Urine PK ^f	X	X							X		X	X	X	X	X	X	
Biomarker		X														X	
Spirometry	X ^g								X			X		X		X	
Magnetic stimulated contraction		X							X				X			X	
Dynamometry	X	X							X		X	X	X	X	X	X	
Muscle biopsy ^h		X															
IPSS ⁱ	X									X			X	X	X		X

	CRU Inpatient																FU
Day	Non-PK Days 2-6, 8-13	PK Days 7 and 14											D15	D16	D17	D18	D20
Hour		0	0.25	0.50	1	1.5	2	3	4	6	8	12	0	0	0	0	4
Urinary system Ultrasound ^j	X									X						X	
MTR-601 administration	X	X															
Adverse events																	
Concomitant medications																	
CRU check-out/discharge																X	
Follow-up telephone call																	X

Abbreviations: AE = adverse event; CK-MB = creatinine kinase heart; CK-MM = creatinine kinase skeletal muscle; D = Day; ECG = electrocardiogram; LVEF = left ventricular ejection fraction; PK = pharmacokinetics.

Note: When several assessments overlap, the suggested sequence of events will be as follows: ECG, vital sign collection, PK sample collection, laboratory blood sample collections, spirometry, dynamometry, urinalysis sample collection, and biopsy, such that PK sample collection will be drawn as close to the nominal collection time point as possible.

- Height measured only at screening.
- Laboratory assessments will include serum chemistry, hematology, liver function tests, coagulation, and creatinine kinase (CK-MM and CK-MB). eGFR will use CKD-EPI calculation.
- Echocardiogram performed on Day 6 and Day 13 only, post AM dosing.
- Telemetry and oximetry will continue from Day 1 into pre-dose Day 2; Day 7 into pre-dose Day 8; and Day 14 into Day 15, and for 12 hours post dosing on all other dosing days although it may be interrupted as needed to allow subjects to bathe.

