- Plasma PK samples will be drawn at pre-dose (time 0) on Days 7 and 14; post-dose on Days 7 and 14 at 1, 1.5, 2, 4, 6, 8 and 12 hours; (need trough at D14) 336 hours post-dose (Day 15); 360 hours post-dose (Day 16); and 384 hours post-dose (Day 17). For Cohorts 3-6, PK samples will also be drawn on Day 2 and Day 8 (both pre-dose).
- Urine will be collected for PK analysis on 12-24 hours post-dose on Day 2; Day 7 and 14 from a pre-dose void and post-dose from 0-4 hours, 4-8 hours, 8-12 hours, and 12-24 hours; from 24-48 hours post-dose; from 48-72 hours post-dose; and from 72-96 hours post-dose. Samples are to be collected at intervals under colored lighting into opaque containers to blind participants to any discoloration of the urine.
- Spirometry performed on Days 2, 8, 10, and 12.
- Mandatory muscle biopsy on Day 14 (time 0) only.
- IPSS questionnaire will be performed at the specified timepoints per SOA- results greater than 8 will necessitate an unscheduled urinary system ultrasound as soon as is feasible.
- Urinary system Ultrasound will be performed at day 3, and days 7 and 14 at the 6-hour timepoint unless the IPSS result (greater than 8) necessitates additional unscheduled ultrasonography.
- Serum chemistry, eGFR, and calcium only.

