8.3. Safety Assessments

Safety assessments ([Table 8](#)) will include AEs and SAEs, as well as physical examinations, clinical laboratory evaluations, vital sign measurements, spirometry, urinary system ultrasound, Echocardiography, and ECGs. Not every assessment will be performed at each visit. Refer to the Schedule of Assessments ([Table 1](#), [Table 2](#), and [Table 3](#)) for specific procedures/assessments and timing. A separate schedule of permitted visit windows for each procedure/assessment will be provided in the Clinical Monitoring Plan and Data Management Plan

Note: When several assessments overlap, the suggested sequence of events will be as follows: ECG, vital sign collection, PK sample collection, laboratory blood sample collections, spirometry, dynamometry, urinalysis sample collection, and biopsy such that PK sample collection will be drawn as close to the nominal collection time point as possible. Echocardiography and Urinary system ultrasounds can be performed last so as to not delay the PK assessments.

Table 8: Safety Assessments

Assessment	Details
AE monitoring	Adverse events will be recorded from the first study medication dose through 14 days after the last follow-up visit/call. AEs will be graded using the scale in Section 8.4.4.3.
Physical examination	Physical examination and review of relevant systems at screening, including body weight and height. Symptom-directed physical examinations and weight measurements are to be performed at other time points or as clinically indicated.
Neurological exam	Includes cranial nerve assessments II-XII, cerebellar function (finger to nose and gait), reflexes (bilateral bicep, patellar, and ankle), gross assessment of extremity strength.
Vital signs	Systolic and diastolic blood pressure, heart rate, respiratory rate, and body temperature.
12-lead Electrocardiograms	The QTcF must be recorded for each ECG. All ECGs must be performed in triplicate with at least a 5 minute rest in the supine position with a minimum of 60 seconds in between and the average value will be used for interpretation and AE grade.
Left ventricular ejection fraction (LVEF)/ echocardiogram	An echocardiogram will measure ventricular volumes and left ventricular ejection fraction.

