Cardiac telemetry, and oximetry	Telemetry and digit oximetry will be monitored by applying at least 1 hour prior to dose administration and remain on for approximately 24 hours in the SAD cohorts. In MAD cohorts, telemetry and digit oximetry will be monitored for approximately 24 hours starting on Day 1, Day 7, and Day 14, and monitored on all dosing days from pre-dose until 12 hours post-dose for the duration of the study. Telemetry and oximetry will be interrupted to accommodate daily hygienic routines (e.g., showering).

Assessment	Details
Spirometry	
Three (3) repetitions with full effort, seated, with approximately 1 minute resting period between each trial (report mean values).
 
A reduction in the vital capacity to less than 80% of the predicted vital capacity with good expiratory effort may suggest diaphragm weakness or paralysis
 
Spirometry measurements will include:
 
Forced expiratory volume in one second (FEV₁).
 
Forced vital capacity (FVC).
 
FEV₁/FVC ratio (FEV₁ divided by FVC).
 
Reference: Graham [5].

Renal function and Urinary tract evaluations	
eGFR will be calculated with each serum chemistry determination. Monitoring the renal function tests will include serum creatinine, BUN, Cystatin C (in select cohorts) serum sodium, potassium, calcium, in addition to the above stated eGFR.
 
Ultrasound will be performed to assess post-void bladder volume in excess of 100 mL and for any evidence of hydronephrosis. The ultrasound will include the kidneys, ureter and bladder.

Electronic nerve stimulation response	The stimulation will be provided by MagSTIM200 ² and response measured.
Dynamometry	
Dynamometry measurements will include:
 
 Grip strength measured with the Jamar device Upper extremity (forearm extension/flexion) and lower extremity (knee extension in sitting position), measured with the microFET2 device. 
Measured up to 3 times and record the best effort. Once with good effort is the intent. However, if not deemed a good effort or there is an interruption in the assessment or mistake on the first tries then it can be repeated up to 3 times.

Pregnancy test or FSH	
For women of childbearing potential: Serum pregnancy test at screening and day of check-in.
 
For postmenopausal women who are not surgically sterile: FSH testing.

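### MAD 12-lead ECGs are scheduled only pre-dose or off drug, so the QTc stopping rule is insensitive to an effect near Cmax

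*Protocol*

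**What the plan says.** Protocol 4.1, Table 5, sets the QTc criterion as "QTcB and QTcF > 500 msec or change from baseline: QTc > 60 msec". One subject meeting it stops that subject; two stop the cohort or escalation. Table 8 (Protocol 8.3) defines the measurement: "All ECGs must be performed in triplicate with at least a 5 minute rest in the supine position", with the average used for interpretation.

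The MAD ECG rows in Table 3 (Protocol 1.5) carry marks at:

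- screening and Day -1, with every Day 1 cell from hour 0 to hour 12 empty;
- hour 0 of Days 7 and 14;
- Day 18.

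Hour 0 is before dosing: "Plasma PK samples will be drawn at pre-dose (time 0) on Days 7 and 14". Plasma PK is also sampled "post-dose on Days 7 and 14 at 1, 1.5, 2, 4, 6, 8 and 12 hours", so staff are already with the subject at those hours.

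Telemetry is "monitored on all dosing days from pre-dose until 12 hours post-dose for the duration of the study", and for about 24 h from Days 1, 7 and 14. No QTc measurement from telemetry is specified.

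SAP 5.16.4 tabulates QTcB and QTcF by visit, but takes the ECG-interpretation shift only to the end-of-study or early-termination visit. SAP 5.16.5 and 5.16.6 summarise the physical and neurological examinations at end of study. SAP 5.16.2 and 5.16.7 already give laboratory and spirometry shifts at each follow-up visit.

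**The concern.** A QTc stopping rule can act only on the QTc values it is given. Both scheduled on-drug values in MAD are troughs, and the Day 18 value is nearly drug-free. An effect above 60 msec near Cmax that has faded by the next morning would not trip the rule.

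This matters most for the later MAD cohorts. Protocol 4.1 lets exposure rise to half of the rat NOAEL exposure. Protocol 2.3 puts steady state at 20 mg at about 1/15 of NOAEL, so the ceiling is 7.5 times the highest repeat-dose exposure in the interim review. The reassuring interim ECG findings for MAD 10 and 20 mg came from cohorts on this pre-dose schedule.

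The SAP point is about reporting only and does not affect stopping decisions. The end-of-study summaries for ECG interpretation and the examinations describe MAD subjects about 96 h off drug, although hour-0 data on Days 7 and 14 are collected.

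**Working it through.** **1. Count of scheduled post-dose assessments.** From Table 3, hours 0.25 to 12 on Days 1, 7 and 14:

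- vital signs at 1, 1.5, 4, 6, 8 and 12 h: 6 × 3 = 18;
- spirometry at 4 and 12 h: 2 × 3 = 6;
- 12-lead ECG: 0.

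The vital-signs row fills the post-dose columns, so the empty ECG cells are not an artefact of column alignment.

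**2. What a pre-dose ECG sees.** The plan states no figure for this. The documents give only accumulation below 2-fold (Protocol 2.3). Assumed: one-compartment oral kinetics, accumulation R of 1.25 to 2.0, single-dose Tmax of 1 to 8 h, and a QTc effect linear in concentration without delay. The elimination rate k comes from R = 1/(1 − exp(−24k)), giving half-lives of 10.3, 15.1 and 24.0 h for R = 1.25, 1.5 and 2.0. The absorption rate is set to give the stated Tmax.

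Fraction of steady-state peak, for Tmax 1 / 4 / 8 h:

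| R | Pre-dose | 4 h post-dose |
|---|---|---|
| 1.25 | 0.217 / 0.285 / 0.442 | 0.828 / 0.997 / 0.945 |
| 1.5 | 0.351 / 0.415 / 0.532 | 0.877 / 0.995 / 0.964 |
| 2.0 | 0.516 / 0.567 / 0.646 | 0.919 / 0.993 / 0.982 |

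For a true 60 msec effect at peak:

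- pre-dose: 60 × 0.217 = 13 to 60 × 0.646 = 39 msec; mid case 60 × 0.415 = 25 msec;
- Day 18: at most 0.0807 of the Day 14 peak, 60 × 0.0807 = 4.8 msec;
- 4 h post-dose: 60 × 0.828 = 49.7 to 60 × 0.997 = 59.8 msec;
- the PK hour equal to Tmax: at least 0.981 of peak, so 58.9 msec or more.

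The Day 7 peak is at least 0.9915 of the steady-state peak in every case.

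**3. Cross-check by a second route.** The exposure cap gives Cmax/Cavg = 421/(6,600/24) = 421/275 = 1.53. If 20 mg is 1/15 of NOAEL for both Cmax and AUC, the human profile has about the same ratio. With instantaneous absorption that implies R of about 1.66 and trough/peak of about 0.40, inside the range above and towards its lower half.

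**4. Effect on the rule.** For a trough ECG to show 60 msec, the peak change must be 60/0.4 = 150, 60/0.5 = 120 or 60/0.6 = 100 msec.

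For the two-subject cohort rule with 6 active subjects, suppose a mean peak change of 60 msec, SD 8 to 12 msec, and independent readings on Days 7 and 14 (all assumed):

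- Both near peak: each reading exceeds 60 with probability 0.5, so a subject triggers with 1 − 0.5² = 0.75, and P(at least 2 of 6) = 1 − 0.25⁶ − 6 × 0.75 × 0.25⁵ = 0.995.
- Both at trough: at most 0.027 (trough/peak 0.6, SD 12), and at most 0.002 at trough/peak 0.5.
- One near peak only, ignoring any contribution from the trough reading: P(at least 2 of 6) = 1 − 7 × 0.5⁶ = 0.891.

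**5. Exposure already covered.** As fractions of NOAEL, with dose linearity from 20 mg = 1/15 and accumulation of 1.25 to 2.0:

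| Dose | Fraction of NOAEL |
|---|---|
| MAD 40 mg | 2/15 = 0.133 |
| MAD 80 mg | 4/15 = 0.267 |
| Single 80 mg | 0.267/1.25 = 0.213 down to 0.267/2.0 = 0.133 |
| Single 160 mg | 0.427 down to 0.267 |
| Ceiling | 0.5 |

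The ceiling is 0.5/0.213 = 2.3 to 0.5/0.133 = 3.75 times the peak of the single 80 mg dose already given. MAD 40 mg is not a new peak. MAD 80 mg and MAD 6 are new peaks unless the single 160 mg dose is given first.

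**The case against.** The strongest reply is that this is a minor gap with layered cover. Subjects are inpatients on telemetry for at least 12 h after every dose. Table 5 is not confined to scheduled ECGs, so an unscheduled recording can trigger it. The Safety Review Committee reviews aggregate ECG data, and a trough shift of about 25 msec across six active subjects would be open to its judgement. No QT signal is reported: the interim review found no clinically significant ECG abnormality, and the adverse events of special interest are not cardiac. Single doses may also have covered the relevant peaks. The ECG rows for SAD Levels 1, 3, 4 and 5, and the upper rows of the first page of Table 2, were not in the text available for this review; nor was the schematic that might show cohort order.

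Much of this stands, and it is why the rule is called insensitive and not blind. SAD cover is not judged here, and only the available text can be said to leave the order of SAD Level 5 and MAD 5 and 6 open. But telemetry has no defined QTc reading, and a committee acting on sub-threshold trough shifts is using judgement, not the rule.

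The modelling can also be faulted. Tmax is assumed, and R = 2.0 sits at the edge of what is reported: with Tmax 8 h it implies Cmax accumulation of 2.13, and the 65% corner implies a peak-to-average ratio of 1.17 against the 1.53 derived above. Removing that corner pushes trough/peak down, which widens the gap. A delayed QTc effect would narrow it.

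**Conclusion.** The concern holds. The schedule fact is exact: no MAD 12-lead ECG is planned from 0.25 to 12 h after any dose, and both on-drug readings are troughs. Its size depends on assumptions. Under the stated kinetics the scheduled ECG sees 22% to 65% of peak, and a 60 msec peak effect reads about 13 to 39 msec, so it would not meet the change criterion on average. Tmax, QTc variability and the shape of the concentration–QTc relation are not in the documents, so confidence in the size is medium. The consequence is greatest for MAD 5 and 6. The SAP shift-table point also holds, but it is a reporting matter.

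**What to change.** 1. **Protocol, Table 3, MAD cohorts 4 to 6.** Record the existing Day 7 triplicate ECG at the scheduled post-dose PK hour (1, 1.5, 2, 4, 6, 8 or 12 h) nearest the Tmax seen in earlier cohorts. Keep Day 14 at pre-dose as the trough reading. Day 7 is at least 99% of steady state under the assumptions, and seven doses (Days 8 to 14) remain on which the individual rule can act. No procedure is added, and the existing order already puts the ECG ahead of the PK draw: "the suggested sequence of events will be as follows: ECG, vital sign collection, PK sample collection". The costs are a protocol amendment with IRB approval and loss of the Day 7 pre-dose reading, which could have held that day's dose. Days 1 to 6 remain without an ECG.

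2. **SAP 5.16.4 to 5.16.6 (lesser).** Show ECG-interpretation, physical and neurological shifts from baseline to each scheduled post-baseline visit, including Days 7 and 14, as is already done for laboratory and spirometry data. The cost is SAP wording and a few table columns from data already collected.
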